The sample consisted of 36 women and 13 men, divided into two age groups: young people between 18 and 30 years old ($22,438 \pm 3,898$) and adults between 31 and 64 years old ($50,212 \pm 9,633$). In terms of origin, 23 were residents of Plasencia (Spain) and 26 in Castelo Branco (Portugal). The descriptive characteristics of the sample are detailed in Table 1.

Table 1. Descriptive characteristics of the sample.

VARIABLES	Total n=49	Origin	Young Men (mean±SD)	Adult Men (mean±SD)	Young Women (mean±SD)	Adult women (mean±SD)
AGE (years)	41,143± 15,485	Spain Portugal	20±2,828 26±NP	46,333±13.317 46,857±10,495	24,111±3,723 19±2	49±9,367 53.50±8.609
	70,545± 12,705	Spain Portugal	80±14,142 69±NP	87,333±17,926 80,714±11,572	68,667±13,684 66,750±8,995	64,411±7,193 66.857±11.016
HEIGHT (m)	1,664±0 ,085	Spain Portugal	1.82±0.113 1.7±NP	1.733±0.025 1.757±0.060	1,652±0.074 1.657±0.049	1.618±0.068 1,616±0.057
	25,404± 3,626	Spain Portugal	24,026±1,280 23,875±np	29,170±6,725 26,148±3,488	25,069±4,334 24,372±3,837	24,611±2,350 25,552±3,548

n: sample size; SD, standard deviation; NP: Not applicable; kg: kilogram; M: Metro; BMI, body mass index; m^2 : Square meter.

Randomization, masking, and experimental design

Participants were randomly assigned to distinct groups using free software Epidat 4.0 (2011, Galicia, Spain). The blinding was double-blind, so that neither the investigators nor the participants knew the group assigned to the participant until the completion of the study and statistical analysis.

The total number of participants was divided into three groups: a control group (T0) (n=12), in which no participants had a skin infection, and two different treatment groups (T1 and T2) (n=37), with diverse levels of EC. The rest of the participants were included in these two treatment groups, including both infected (n=32) and healthy (n=5) participants. Thus, group T1 (n=25) had 23 participants with infection and 2 healthy participants, and group T2 (n=12) had 9 participants with infection and 3 healthy participants.

The clinical evaluation of the participants was carried out before the start of treatment and, subsequently, on days 15, 30, 45 and 60 of treatment, except for cultures, both mycological and bacterial, which were performed at baseline, at 30 days and at 60 days of treatment. All reviews, sampling, and data collected were performed by the same observer.

Choice of EO, base cream, and preparation of treatments

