After reviewing the available literature, the essential oil (EO) of *M. alternifolia* was chosen for its antibacterial and antifungal characteristics (16–19). There were 3 types of commercial *M. alternifolia* EO from the brands Marnys® (Cartagena, Spain), Naissance® (Neath, United Kingdom) and Esencias Lozano® (Murcia, Spain). However, the choice of the specific commercial EO depended on the results obtained from the analysis of its composition. This analysis was performed using gas chromatography mass spectrometry (CG-MS) and the results obtained were contrasted with those available in the online database SpectraBase (WILEY, John Wiley & Sons).

The cream used as a base for the incorporation of the different concentrations of EO tested was a hand and nail cream (*La Chinata*®, Plasencia, Spain), in which Extra Virgin Olive Oil is used. This cream was chosen after verifying that none of its components were allergens for the skin of the participants according to Regulation 1223/2009(1). In addition, it was the treatment received by patients in the T0 group, in whom no type of EC was added.

To test the possible efficacy of the chosen *M. alternifolia* EO as a treatment against infections, the base cream was enriched with different concentrations of EO. Specifically, 1% for the T1 treatment group

and 0.5% for the T2 treatment group. The emulsion of the EO and the base cream was carried out by means of a magnetic stirrer (Agimatic-N, Barcelona, Spain) under sterile conditions (laminar flow cabinet, Telstar AV-100), adding the necessary volume of EC until the desired two concentrations were achieved.

Treatments were administered to participants in the form of prefilled 15ml syringes under sterile conditions with enough for 15 days of treatment. Along with the treatment, all the necessary information was provided on the hygienic habits to follow (washing the feet properly with soap and water and drying them properly with a towel for exclusive use), the correct way of applying the treatment, the daily volume of treatment for each foot (0.5ml/2 times a day).

Exploration, sampling, and diagnostic tests

Sociodemographic data (age and sex), medical and podiatric history, allergies and pharmacological treatments prescribed, as well as hygiene habits, were obtained through the completion of a Google Forms survey (Annex 2).

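### The double-blind claim is not supported for contrasts with T0: infection status identifies oil with certainty for 32 of 49 participants and classifies oil v plain cream correctly for 44 of 49

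*Combined protocol and SAP*

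**What the plan says.** Type of study, permits, and inclusion criteria describes the whole trial as randomized and double-blind. Randomization, masking, and experimental design repeats this without exception: "neither the investigators nor the participants knew the group assigned to the participant until the completion of the study". On allocation it says: "Participants were randomly assigned to distinct groups using free software Epidat 4.0". No stratification or restriction by infection status is described.

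The next paragraph of that section gives the composition of the groups. There is "a control group (T0) (n=12), in which no participants had a skin infection". The two oil groups take everyone else, "including both infected (n=32) and healthy (n=5) participants". By group, "group T1 (n=25) had 23 participants with infection and 2 healthy participants". For the lower concentration the text gives: "group T2 (n=12) had 9 participants with infection and 3 healthy participants".

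The section ends: "All reviews, sampling, and data collected were performed by the same observer". Choice of EO, base cream, and preparation of treatments adds that the base cream without oil is the control: "it was the treatment received by patients in the T0 group".

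Variables and statistical analysis uses T0 as comparator for hydration. Efficacy of treatments compares remission of infection between T1 and T2 only.

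**The concern.** Masking of the assessor works only if nothing the assessor learns about a participant points to the group. Here infection status does point to it. Anyone who knows that a participant is infected, and knows how the groups were composed, knows that the participant is receiving oil. The person who examined and sampled the feet is also the person who took the hydration readings.

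Hydration is the only outcome on which the report compares oil with a control. Tables 11 and 12 sit under a trial-wide double-blind label, so a reader would credit those contrasts with protection against observer influence that the design does not secure.

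**Working it through.** **Inputs** (Randomization, masking, and experimental design)

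| | T0, plain cream | T1, 1% | T2, 0.5% | Total |
|---|---|---|---|---|
| Infected | 0 | 23 | 9 | 32 |
| Uninfected | 12 | 2 | 3 | 17 |
| Total | 12 | 25 | 12 | 49 |

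**Reproducing the stated figures.** 12 + 25 + 12 = 49 participants; 23 + 9 = 32 infected; 32/49 = 65.3%, as given under Test results for microbiological diagnostics. Table 6 counts 8 fungal and 20 bacterial infections, so at most 8 + 20 = 28 infected people, which does not agree with 32. I use 32 because the group description, the microbiology text and Table 3 all give it. The mechanism needs only that T0 contains no infected participant.

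**What infection status tells about oil v plain cream**

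- Conclusive: all 32 infected participants are on oil, so 32/49 = 65.3% are identified with certainty.
- Uninfected: 12 of 17 are in T0, so the chance of plain cream is 12/17 = 70.6%, and of oil 5/17 = 29.4%.
- Best guess (infected = oil, uninfected = plain cream): (32 + 12)/49 = 44/49 = 89.8%.
- Benchmark of always guessing oil: 37/49 = 75.5%.
- Exact group among three (infected guessed T1, uninfected guessed T0): (23 + 12)/49 = 35/49 = 71.4%. Status does not separate T1 from T2 with any certainty.

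**Could chance have produced this?** If the 12 T0 places were an unrestricted random draw from the 49 analysed, the probability that all 12 are uninfected is C(17,12)/C(49,12) = 6.7 × 10⁻⁸, about 7 in 100 million. Infection status almost certainly entered the formation of T0, so someone used it. The text does not say who, or whether that person was separate from the observer.

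**Timing.** Exploration, sampling, and diagnostic tests gives 1 to 3 days for bacterial culture and 2 to 4 weeks for mycological culture. The longest wait, 4 × 7 = 28 days, ends before days 45 and 60. Those are the visits with significant contrasts against T0 (right outer arch; adjusted p in Table 12: T0 v T1 0.023 at day 45; T0 v T1 0.024 and T0 v T2 0.002 at day 60). The running text gives 0.016, 0.021 and 0.003 for the same three contrasts, which does not change which are significant. Baseline results could therefore have been available before those readings.

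**Participants lost.** The counts cover the 49 analysed. The group and infection status of the 7 who did not attend review are not in the readable text. If the best-guess rule were wrong or right for all 7, its accuracy among 56 would run from 44/56 = 78.6% to 51/56 = 91.1%.

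**The case against.** The strongest reply is that the observer's knowledge is inferred. The text does not say that the observer read the cultures, was told the results, or knew that T0 was free of infection. Infection was defined by two positive tests, so looking at the feet would not establish it. Wood's light was recorded at every review, but it showed only two colours, attributed to two organisms, whereas the cultures found several others. This stands. It rules out saying that the observer was unmasked, but it does not rescue a blanket claim, because no safeguard is described that would have kept status or the placement pattern from the person doing all the sampling and measuring.

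The reach is also limited. Hydration is read by an instrument with a stated accuracy of ±3%, with three readings per point. The significant group differences are at one site and favour T0, so an observer inclined towards the oil would have pushed the other way. This limits the likely bias without showing that masking held.

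A reader might go further in three ways that the documents do not support:

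- That infection status reveals the group for 90%. The 90% is best-guess accuracy for oil v plain cream. Certainty applies to 65%, and the three groups are not distinguished.
- That smell or appearance gave the oil away, to participants as well. The readable text says nothing about either; it describes prefilled syringes, with no different container for T0. Nor does it say that participants knew the placement pattern.
- That the T0 contrasts were in fact unmasked, and that masking demonstrably covered concentration. Neither is established.

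**Conclusion.** The trial-wide double-blind statement is not supported for contrasts with T0. Infection status fixes oil for 32/49 (65%) and classifies oil v plain cream correctly for 44/49 (90%, against 76% for always guessing oil). The hydration readings were taken by the person who examined and sampled the feet. Masking against T0 is compromised and not shown to hold; that it was broken is not proven.

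This rests on the stated group counts for the 49 analysed. For actual unmasking it would also need the observer to have known both infection status and the placement pattern, on which the documents are silent. The T1 v T2 remission comparison is not affected by this mechanism.

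The same counts show a further limit. T0 v oil is also a comparison of 0/12 with 32/37 infected, so these contrasts would be confounded with infection status even under perfect masking.

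**What to change.** In Type of study, permits, and inclusion criteria and in Randomization, masking, and experimental design, limit the double-blind statement to T1 v T2, worded as the authors' own claim. Then add, for example: *All 32 infected participants were in the oil groups and none in T0. Infection status therefore identified oil with certainty for 32/49 participants and classified oil v plain cream correctly for 44/49. Masking of oil v plain cream is compromised by this and has not been shown to hold.*

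In Variables and statistical analysis, and with the hydration results in Tables 11 and 12, do not present contrasts with T0 as double-blind evidence. State there that they are confounded with infection status (0/12 v 32/37), which rewording does not cure.

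If records exist, also state who held the allocation list and what the observer knew of culture results and group composition, and when.

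The cost is wording only. The downside is that the stated quality of the T0 comparison becomes less favourable.

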Statistical analysis was performed using the statistical analysis program IBM-SPSS Statistics for Windows version 25 (IBM Corp. Armonk, NY, USA). Some figures have been obtained using the Python programming language, using the Seaborn library (Waskom, M. L., (2021). Seaborn: statistical data visualization. *Journal of Open-Source Software*, 6(60), 3021, <https://doi.org/10.21105/joss.03021>).

Normality was assessed using the Shapiro-Wilk test. To evaluate the influence of different variables on infection remission, a Cox regression model was used, and survival curves of significant factors were plotted. To compare the efficacy of different EC concentrations, survival curves were compared using the Log-rank test. The Mann-Whitney U test was used to assess hydration averages according to sex. To check if there were improvements in hydration due to the use of the cream with different concentrations of EC (T1 and T2) compared to the control group (T0), hydration levels were compared using Kruskal-Wallis tests, using the Mann-Whitney U test with correction of p-values by the Bonferroni method for multiple comparisons.

In all statistical tests, significance was considered when p-value<0.05 and high significance when p-value<0.01.

2. Results

Analysis of the Elemental Composition of Commercial S. S.

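### No infected participant received the oil-free cream (T0: 0 of 12 infected), so infection remission cannot be attributed to the oil, and T0 is not a randomised control for remission

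*Combined protocol and SAP*

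**What the plan says.** All references are to the combined protocol and SAP. It uses both EO and EC for the essential oil.

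- **Allocation** (Section 1, *Randomization, masking, and experimental design*): "Participants were randomly assigned to distinct groups using free software Epidat 4.0". The same section then gives "a control group (T0) (n=12), in which no participants had a skin infection". It continues: "The rest of the participants were included in these two treatment groups, including both infected (n=32) and healthy (n=5) participants". Specifically, "group T1 (n=25) had 23 participants with infection and 2 healthy participants", and T2 (n=12) had 9 infected and 3 healthy.
- **What T0 received** (Section 1, *Choice of EO, base cream, and preparation of treatments*): of the base cream it says "it was the treatment received by patients in the T0 group, in whom no type of EC was added". T1 received 1% oil and T2 received 0.5%. Hygiene instructions were handed out along with the cream.
- **Aim** (same section): the purpose given is to test the efficacy of the chosen "EO as a treatment against infections, the base cream was enriched with different concentrations of EO".
- **Planned remission analysis** (*Variables and statistical analysis*): "To compare the efficacy of different EC concentrations, survival curves were compared using the Log-rank test".
- **Planned hydration analysis** (same section): Kruskal-Wallis tests across T0, T1 and T2, then Bonferroni-corrected Mann-Whitney tests. Infection status is not part of the analysis.
- **Results** (Section 2, *Efficacy of treatments*): the question of whether the enriched cream works is approached by plotting T1 and T2 only. For fungal infection (p=0.611) the text concludes that the two concentrations are alike in efficacy. For bacterial infection (p=0.130) it calls the 0.5% group the better one, and notes in the same sentence that the difference was not significant.

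**The concern.** A control group answers the efficacy question only if its members could have had the outcome. Nobody in T0 had an infection, so nobody in T0 could remit. Everyone who could remit received oil. The contrast needed for the stated aim, oil against base cream in infected people, has no participants on one side.

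Two further matters follow from the same counts. First, a reader told that assignment was random would take T0 as comparable with T1 and T2 at baseline. On infection status it is not, and the text does not say how this arose. Second, hydration is the only outcome in which T0 is compared with the oil groups. That comparison sets a group with no infection against groups that are mostly infected, without allowing for it.

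At stake is whether the trial can say anything about the oil as a treatment for foot infection.

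**Working it through.** **1. Reproduce the counts.** Inputs are from *Randomization, masking, and experimental design*.

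| Group | Cream | Infected | Healthy | Share infected |
|---|---|---|---|---|
| T0 | base, no oil | 0 | 12 | 0% |
| T1 | 1% oil | 23 | 2 | 23/25 = 92% |
| T2 | 0.5% oil | 9 | 3 | 9/12 = 75% |
| Total | | 32 | 17 | 32/49 = 65.3% |

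The total agrees with the 32 (65.3%) given under *Test results for microbiological diagnostics*.

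**2. Who supports an oil versus base-cream contrast for remission?** Infected with oil: 23 + 9 = 32. Infected without oil: 0. No re-analysis of these data can fill the empty cell.

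**3. Does the 1% versus 0.5% comparison substitute for it?** Both arms contain oil, so it can show at most a difference between concentrations. Taking Tables 4 and 5 as printed, the order reverses. Mean time is shorter with 1% for fungal infection (11.61 v 14.00 days) and shorter with 0.5% for bacterial infection (44.82 v 49.35 days). Neither test is significant (p=0.611 and p=0.130). There is no consistent gradient from which an oil effect could be argued. A non-significant test does not establish similarity either.

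**4. Is 0 of 12 compatible with simple randomisation of everyone?**

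- Expected infected in T0: 12 × 32/49 = 7.84.
- Probability of none among the 49 completers: C(17,12)/C(49,12) = 6,188/92,263,734,836 = 6.7e-8.
- Allowance for dropouts: *Sample* reports 7 of 56 excluded for not attending review. The available text does not give their group or infection status, so every placement was tried. The largest probability arises if 6 were infected and in T0 and 1 was uninfected and in another group. T0 then has 6 infected of 18, and 38 of 56 are infected overall. The probability of 6 or fewer infected in T0 is 2.6e-4.

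**5. Hydration.** The groups compared are 0%, 92% and 75% infected. Hydration by infection status is not reported, so the size and direction of any confounding cannot be calculated. Table 11 gives no clear hint:

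| Point and time | T0 − T1 | T0 − T2 |
|---|---|---|
| Right external arch, baseline | 20.622 − 19.081 = 1.5 | 20.622 − 15.119 = 5.5 |
| Right digital plantar, baseline | 29.630 − 26.538 = 3.1 | 29.630 − 28.846 = 0.8 |
| Right external arch, day 45 | 29.243 − 18.564 = 10.7 | 29.243 − 20.989 = 8.3 |

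The more heavily infected arm is sometimes nearer to T0 and sometimes further away.

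**6. Could an uninfected-only hydration analysis help?** It would compare 12 with 2 (T1) and 12 with 3 (T2). The smallest attainable two-sided exact Mann-Whitney p-values are:

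- T0 v T1: 2/C(14,2) = 2/91 = 0.022, or 0.066 after Bonferroni × 3. It can never reach 0.05.
- T0 v T2: 2/C(15,3) = 2/455 = 0.0044, or 0.013 after Bonferroni × 3.

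**The case against.** Much of the case on the other side is fair.

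- **The document is open about T0.** It states that T0 had no infections, and it makes no remission comparison with T0. A reader might infer that the report claims the oil outperformed the base cream. No sentence in the available text says so: the formal tests are between concentrations, and the results speak of the enriched cream. This stands. But the aim is framed as efficacy of the oil, and the results pose an effectiveness question that only an oil-free infected group could answer, so the limit has to be stated.
- **The description of 0.5% as better is already qualified** by the non-significance in the same sentence. This stands; the wording is loose rather than concealed. The conclusion of like efficacy for fungal infection has no such rescue, because it is drawn from the non-significant result.
- **The probability tests a model that may not have been used.** A reader might infer that randomisation was not done or was broken. The documents do not support that. Separate allocation within infection status, or a deliberate choice to keep T0 uninfected, would fit the counts, and Figure 1 is not available. The probability shows only that simple randomisation of all participants is not the explanation. It does not measure bias.
- **The hydration result goes against the oil,** since T0 had the greater hydration where differences were found, so it supports no claim of benefit. The groups are also described as similar at baseline, with printed p-values of 0.107 or more. A reader might infer that the hydration comparison is shown to be biased; it is not. Equally, non-significance in groups of 12, 25 and 12 does not show that infection status is harmless.

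**Conclusion.** The point holds and is wrong as written. The trial has no infected participant on oil-free cream (0 of 12 in T0; all 32 infected in T1 or T2). It therefore cannot show that the oil, rather than the base cream, the hygiene instructions or natural course, produced remission. This rests only on the printed counts and on T0 alone receiving the plain cream. It does not depend on how allocation was done.

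The allocation statement is incomplete. Simple randomisation of all participants does not account for the pattern (6.7e-8 among completers, at most 2.6e-4 over all placements of the 7 dropouts), and the available text gives no other rule.

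For hydration the conclusion is limited: the contrasts with T0 are confounded with infection status by design, with size and direction unknown.

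**What to change.** 1. Describe T0 as an uninfected reference group, not as a randomised control for infection remission. State the rule by which people entered T0, T1 and T2, and whether infection status was part of it.
2. Report remission in T1 and T2 as uncontrolled before-after results, plus a 1% versus 0.5% contrast among participants infected at baseline. State that no effect of the oil over the base cream can be inferred. Replace the conclusion of like efficacy (p=0.611) and the description of 0.5% as better (p=0.130) with a statement that no difference was shown.
3. Add a caveat that the T0 versus T1 and T2 hydration contrasts are exploratory and confounded with infection status (0% against 92% and 75% infected), with size and direction unknown. An infection-adjusted or uninfected-only analysis is optional. Only 5 oil-treated participants were uninfected, so it would tell little.

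The cost is rewording; no new participants or data are needed. The downside is weaker conclusions, because the oil-efficacy aim is left unanswered.

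The time coding behind Tables 4 and 5, the differing infection counts and the repeated baseline values in Table 11 should be handled as separate points. They have no bearing on this one.
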